10.4 DESCRIPTION OF STATISTICAL METHODS

10.4.1 GENERAL APPROACH

As a small, exploratory, pilot study, we are uncertain the difference, if any, between the two arms in regards to B-lines after treatment. Unless stated otherwise, two-sided p values < 0.05 will be considered statistically significant, without regard to multiple comparisons. Statistical tables and listings and analyses will be produced using SAS® release 9.1 or later (SAS Institute, Inc, Cary, NC, USA) or other validated statistical software.

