10.4.3 ANALYSIS OF THE PRIMARY EFFICACY ENDPOINT(S)

The total number of B-lines at the conclusion of ED AHF management

We will examine the distribution of B-lines measurements for the groups with and without events separately. Both absolute number and relative change will be evaluated. Receiver Operating Characteristic (ROC) curves will be plotted together with area under the curve (AUC) calculated to understand the prediction performance of the B-line measurements. Sensitivity, specificity, positive and negative predictive values will be computed at a number of thresholds of B-line measurements to understand the trade-off between false positive and false negative. Confidence intervals of statistical measures will be constructed using the bootstrap method.⁹¹ Although 15 B-lines have been previously identified as a valid threshold, an alternative number may be more useful in the ED setting.

Potential covariates will also be considered in a logistic regression setting to improve precision, which includes baseline co-morbidities, baseline medications (in particular guideline recommended therapies) in-hospital medications, baseline renal function, serum sodium, natriuretic peptide levels, troponin levels, renal function, baseline blood pressure, and discharge medications. Variables such as physical exam, other vital signs, and hemoconcentration may also be included. These covariates are known markers of risk and are standard of care assessments for the vast majority of AHF admissions. Covariates with univariately significant association with the outcome will be included together with the treatment indicator in a logistic regression model. Due to limited sample size, we will limit the number of covariates (including treatment indicator) such that there is 10 events per covariate.

ANALYSIS OF THE SECONDARY ENDPOINTS

1. Dyspnea will also be assessed using a 5-point and 7-point Likert scale.

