Dyspnea will be assessed at the baseline and 6 hours later (or closest time point prior to ER discharge using two instruments. Dyspnea will also be assessed at any time between D2 and D/C. A 7-point Likert scale to determine change from baseline: 1) markedly worse, 2) moderately worse, 3) minimally worse, 4) no change, 5) minimally improved, 6) moderately improved, 7) markedly improved. However, patients may not recall accurately how they felt at baseline or be uncertain about when baseline was supposed to be. Also, patients with severe symptoms who don't respond and patients whose symptoms were initially mild and have little room to improve may end up with similar change scores. Accordingly, symptoms were also assessed using an absolute scale. Change in dyspnoea can be calculated by subtracting scores. A 5-point Likert scale was used to document patients' current status: 1) not short of breath at all, 2) mildly short of breath, 3) moderately short of breath, 4) severely short of breath, 5) very severely short of breath.

Patients were placed at 45 degrees for all questioning. If patients were recently up and walking, at least 2 minutes of equilibration is required.

Change scores between responses at baseline and 6 hours on the 5-point Likert scale items and the VAS were calculated by subtracting the baseline value from the 6-hour value. These change scores were categorized as improvement, worsening and no change. Fisher's exact tests were used to compare the 3 groups by either definition on changes in the 5-point Likert scale

2. The comparison of binary endpoints (B-lines ≤ 15) will be performed using Chi-square or Fishers exact test, as appropriate.

As 15 B-lines have been previously shown to be associated with worse outcomes, a difference of 15 B lines will be considered significant for this study.

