10.4.4 ANALYSIS OF THE EXPLORATORY ENDPOINT(S)

Exploratory Endpoints	
Total DAOOH through 30 days post-discharge	Association of B-lines at discharge and 30 day outcomes
Time to reach B-lines ≤ 15	Association of baseline, discharge, and change of b-lines with 30 day outcomes
Change in physical exam findings	All Cause readmissions, All cause ED re-visits

DAOOH: Will be compared using T test or Wilcoxon rank-sum test, as appropriate.

If the distribution of 30 day DAOOH is skewed, the T test may not perform satisfactorily. An alternative approach to evaluate the robustness of the analysis, is to treat DAOOH as an ordinal outcome and use the proportional odds (PO) regression model to compare the two arms. The PO model is a generalization of the Wilcoxon (Mann-Whitney) test to estimate the shift in the underlying distribution of DAOOH by the intervention. The PO regression allows for adjustment of baseline covariates to enhance power.

For reproducibility analysis, generalized linear mixed-effects models will be fitted to estimate the inter- and intra-observer variability, where both patients and observers are treated as random effects.

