10.5 SAMPLE SIZE OVERALL

This pilot study is powered to show a difference of at least 7 B-lines between treatment arms. With a total of 70 subjects (i.e. 35 in each arm), we will have 82% power to detect an effect size of 0.7 on the number of B-lines, where the type I error rate is controlled at 0.05 (two sided)..

Local Sample Size: As a multicenter study, the expected enrollment at IU is half the patients or 35. However, up to 50 patients may be enrolled depending on accrual rates at the other site.

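### Section 10.4.3 turns 15 B-lines from a patient-level cut-off into a significant difference, at odds with the p < 0.05 rule and the 7-line design difference

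*Combined protocol and SAP*

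**What the plan says.** The sentence closes the secondary-endpoint part of section 10.4.3, directly after the test for the binary endpoint of 15 B-lines or fewer. Its premise is "As 15 B-lines have been previously shown to be associated with worse outcomes" and its conclusion is that "a difference of 15 B lines will be considered significant for this study".

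Two other sections bear on it:

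- Section 10.4.1: "Unless stated otherwise, two-sided p values < 0.05 will be considered statistically significant".
- Section 10.5: "This pilot study is powered to show a difference of at least 7 B-lines between treatment arms", and, with 35 per arm and a two-sided 0.05 type I error, "we will have 82% power to detect an effect size of 0.7 on the number of B-lines".

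Elsewhere, 15 B-lines is a level of a patient's total count. It is the entry criterion of more than 15 (5.1) and the matching screen-failure reason (5.3). It is the count at which the study protocol ends (4.1), the binary secondary endpoint (4.2.1) and the target in the time-to-event exploratory endpoint (4.2.2, 10.4.4). The primary-endpoint text in 10.4.3 also treats it as a cut-off: "Although 15 B-lines have been previously identified as a valid threshold, an alternative number may be more useful in the ED setting".

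**The concern.** The premise does not lead to the conclusion. That patients with 15 lines do worse says nothing about whether a difference of 15 lines, between arms or over time, is the right yardstick. The sentence also cannot apply to the endpoint it follows, because a comparison of proportions at or below 15 has no difference in lines.

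Its scope is open in three ways:

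- Significance may be statistical or clinical.
- The difference may be between arm means or within a patient. The second is possible because change is also analysed: "Both absolute number and relative change will be evaluated" in 10.4.3 and "Association of baseline, discharge, and change of b-lines with 30 day outcomes" in 10.4.4.
- The endpoint may be the primary count or a secondary one.

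The rule in 10.4.1 allows exceptions, so a reader could take this sentence as one. At stake is how the primary B-line result is read. The trial is unblinded (10.6.1) and is meant to inform a definitive trial (section 3). With three unreconciled yardsticks (p < 0.05, 7 lines and 15 lines), the choice could be made after the result is known.

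**Working it through.** **Inputs.** From 10.5: 35 per arm, difference 7, effect size 0.7, two-sided alpha 0.05, stated power 82%. From 10.4.3: 15 lines. The SD is not stated; it follows as 7 / 0.7 = 10. Normality is assumed.

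**Reproducing the plan's figure.** A two-sample t test with 35 per arm (68 df), effect size 0.7 and two-sided 0.05 has power 82.3% (83.4% by the normal approximation). This matches the stated 82%, so the sample-size arithmetic is sound.

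**Reading 1: between-arm significance criterion.**

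- SE = 10 × √(2/35) = 2.390.
- Smallest observed difference with p < 0.05: t(0.975, 68) × SE = 4.77 lines.
- Observed difference of 7: t = 7 / 2.390 = 2.93, p = 0.0046, 95% CI 7 ± 4.77 = 2.2 to 11.8.
- P(observed ≥ 15 when the truth is 7) = 1 − Φ(8 / 2.390) = 0.04%.
- P(observed ≥ 15 when the truth is 15) = 50% at any SD, as for any observed cut-off placed at the true value.

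In 200,000 simulated normal trials (SD 10, true difference 7), p < 0.05 with an observed difference below 15 occurred in 82.3% with the t test and 80.3% with the Wilcoxon rank-sum test. The choice between these tests makes little difference.

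The table shows sensitivity to the SD. Values above 10 are assumptions and do not fit the plan's own pairing of 7 lines with 0.7.

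| SD | p < 0.05 boundary (lines) | P(observed ≥ 15, truth 7) |
|---|---|---|
| 10 | 4.8 | 0.04% |
| 15 | 7.2 | 1.3% |
| 20 | 9.5 | 4.7% |
| 25 | 11.9 | 9.0% |
| 30 | 14.3 | 13.2% |

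**Reading 2: within-patient change.** Entry requires more than 15 lines. A patient who starts at 16 to 29 and ends at 15 has dropped 1 to 14 lines, so meets the binary endpoint but not a 15-line change. A patient who goes from 40 to 25 has dropped 15 and does not meet the endpoint.

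**Reading 3: between-arm clinical importance.** 7 / 15 = 47%, so the design difference is under half of the difference called important. At SD 10, 15 lines is an effect size of 1.5, for which power is 79.7% with 8 per arm and 84.8% with 9 per arm. The 35 per arm was therefore not sized on 15.

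**The case against.** The strongest reply is that the sentence was never meant as a test criterion. Section 10.4.1 speaks of statistical significance, whereas this sentence says only significant, gives a prognostic reason and names no test. Clinical importance, or a loose restatement of the cut-off just above it, fits that wording at least as well. Powering on 7 while regarding 15 as important is permissible, and at SD 10 the trial has over 99.9% power for a true 15-line difference. A 15-line drop and a final count of 15 or fewer are different measures that will naturally classify some patients differently, and no responder endpoint uses the drop. No entry, treatment or stopping rule uses a 15-line difference, and the trial is a small pilot.

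Much of this stands. The figures under reading 1 are conditional on that reading, and p < 0.05 remains the default. The SD of 10 is implied only. The spread is uncertain, partly because the training material in 17.1 caps a sector at 20 lines and the core-lab text in 17.3 at 10, giving maximum totals of 160 or 80 over eight sectors. At SD 30 the p < 0.05 boundary comes close to 15.

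The reply does not remove the defect. The text does not say that clinical importance is meant, and if it is, the gap between 7 and 15 still needs explaining. If the cut-off was meant, difference is the wrong word. Under every reading the sentence needs correction.

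**Conclusion.** The concern holds. The 15-line difference is an unsupported threshold on the trial's main measure, derived from a patient-level cut-off and not reconciled with p < 0.05 or with the 7-line design difference.

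The size of the conflict depends on the reading. As a between-arm criterion at the implied SD of 10, it would overrule p < 0.05 for observed differences from about 4.8 to just under 15 lines and would almost never be met at the design effect. The boundary stays below 15 at every SD examined, up to 30. As clinical importance, it leaves a factor of about two unexplained. As a within-patient change, it cuts across the binary endpoint.

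The harm is possible misinterpretation of the B-line result. The sample size is not wrong.

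**What to change.** In section 10.4.3, delete the sentence as a significance criterion and keep 15 only as the absolute cut-off for the binary endpoint. Judge the between-arm difference in total B-lines by the two-sided 0.05 rule already in 10.4.1 and 10.5, and report it with its 95% confidence interval.

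If the sponsor wants 15 as a benchmark of clinical importance, label it so. State whether it is between-arm or within-patient and which endpoint it applies to, give a reason for a difference of that size, and explain it against the 7 lines in 10.5.

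The cost is one sentence deleted or rewritten, with no change to sample size, visits or data collected. Stating in 10.5 that the 82% assumes an SD of 10 would help the reader but is a separate matter of detail. The edit also does not supply a named between-arm test for the primary count, which the primary-endpoint text in 10.4.3 lacks.

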10.4.4 ANALYSIS OF THE EXPLORATORY ENDPOINT(S)

Exploratory Endpoints	
Total DAOOH through 30 days post-discharge	Association of B-lines at discharge and 30 day outcomes
Time to reach B-lines ≤ 15	Association of baseline, discharge, and change of b-lines with 30 day outcomes
Change in physical exam findings	All Cause readmissions, All cause ED re-visits

DAOOH: Will be compared using T test or Wilcoxon rank-sum test, as appropriate.

If the distribution of 30 day DAOOH is skewed, the T test may not perform satisfactorily. An alternative approach to evaluate the robustness of the analysis, is to treat DAOOH as an ordinal outcome and use the proportional odds (PO) regression model to compare the two arms. The PO model is a generalization of the Wilcoxon (Mann-Whitney) test to estimate the shift in the underlying distribution of DAOOH by the intervention. The PO regression allows for adjustment of baseline covariates to enhance power.

For reproducibility analysis, generalized linear mixed-effects models will be fitted to estimate the inter- and intra-observer variability, where both patients and observers are treated as random effects.

10.4.5 SAFETY ANALYSES

Hypotensive events will be reported per treatment arm as well as other safety events ascertained during the study. Continuous variables will be summarized by typical parameters such as mean, standard deviation and range and compared using two-sample T test (if the normality assumption holds) or Wilcoxon rank-sum test (if the normality assumption does not hold). Normality of distribution will be determined using the Kolmogorov-Smirnov goodness-of-fit test. Categorical data will be summarized by frequency and percentage and analyzed using the Chi-square or Fishers exact test, as appropriate.

As all cause mortality and re-hospitalizations will already be reported as part of the efficacy exploratory analyses, these will also be highlighted as safety analyses.

10.4.6 ADHERENCE AND RETENTION ANALYSES

Missing data: We will compare relevant patient characteristics between those who stay in the study and those who drop out to examine whether there are characteristics that discriminate between the two groups. It is possible that the dropout mechanism does not depend on unobserved outcomes (Missing At Random, or MAR),⁹⁵ where no bias will be introduced by ignoring the missing-data mechanism. We can simply use all observed outcomes for the analysis. Under circumstances where power loss is of concern, we will use a multiple imputation⁹⁶ procedure to make use of all relevant observed variables to enhance power. The SAS procedure MI and MIANALYZE will be used for implementation of this procedure.

In case the dropouts are Missing Not At Random (MNAR), which means the likelihood of drop-out depends on an unobserved outcome, potential bias can be introduced if the miss-data mechanism is ignored. We will make various assumptions regarding the missing-data process. With these assumptions, we will fit proper models, either in the form of selection model⁹⁷, pattern mixture model⁹⁵, or latent variable model⁹⁸ to account for the missing-data process. A sensitivity analysis will be conducted to compare the results based on different assumptions and models and assess the robustness of the inference.

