6.1.1 DOSING & DOSE ESCALATION

The algorithm below

outlines the treatment protocol.

[^]the protocol was designed to be an ED based protocol. Thus, for patients who leave the ER prior to 6 hours, deviations from the algorithm will NOT be protocol violations.

** ALL enrolled patients will be re-assessed at least twice during their ED stay, unless the patient is discharged from the ER or other clinical priority. First re-assessment will occur within 2-4 hours of first TREATMENT. Assessments outside this window are NOT allowed for study purposes unless at the discretion of the investigator. The second re-assessment will occur EITHER 2-4 hours after the first OR prior to discharge from the ER or at 6 hours after start of treatment. IF the pre-discharge assessment is missed in the ER, if possible, this should occur ASAP after arrival to the hospital floor, unless completed within one hour of the last assessment.

NOTE: the maximum dose allowed at any one time of IV Lasix is 200mg IV.

NOTE: For additional IV loop diuretic doses, the options under Restart Algorithm are three options. Clinical/Research team may choose one of the three loop diuretic dose options.

NOTE: The protocol is not optional by the clinical team. Of course, patient safety comes first, similar to all other interventional trials. However, similar to other interventional studies, once randomized, the study protocol should continue forward.

NOTE: Urine output: An estimated urine output is acceptable.

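### Section 10.4.6 promises no bias under MAR from using observed outcomes as they stand and keeps imputation for power loss; that promise does not hold in general for the plan's unadjusted between-arm tests

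*Combined protocol and SAP*

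**What the plan says.** The missing-data rule is in Section 10.4.6 of the combined protocol and SAP. Under MAR it calls the mechanism one "where no bias will be introduced by ignoring the missing-data mechanism. We can simply use all observed outcomes for the analysis". Imputation enters on a separate condition: "Under circumstances where power loss is of concern, we will use a multiple imputation" procedure, whose purpose is to "make use of all relevant observed variables to enhance power". The section mentions bias as a risk only under MNAR, for which it plans selection, pattern-mixture or latent-variable models and a sensitivity analysis.

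The comparisons that these data feed are mostly unadjusted:

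- Secondary endpoint, in Section 10.4.3: "The comparison of binary endpoints (B-lines ≤ 15) will be performed using Chi-square or Fishers exact test, as appropriate".
- Dyspnea change categories, also in Section 10.4.3: Fisher's exact test.
- Exploratory endpoint, in Section 10.4.4: "DAOOH: Will be compared using T test or Wilcoxon rank-sum test, as appropriate".
- Primary B-line count: Section 10.4.3 names no between-arm test. Section 10.5 gives 82% power for an effect size of 0.7 with 35 per arm, which implies a two-sample comparison.

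Section 6.1.1 accepts that a late scan may be missing: "IF the pre-discharge assessment is missed in the ER, if possible, this should occur ASAP after arrival to the hospital floor".

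**The concern.** MAR means that, given the observed data, missingness does not depend on the unobserved outcome. It may still depend on those observed data. Ignoring the mechanism is then safe for a likelihood or imputation analysis that includes the variables driving missingness. A t, Wilcoxon, chi-square or Fisher test on patients who happen to have the outcome includes none of them. Such a test generally needs the stronger condition that, within each arm, missingness is unrelated to the outcome.

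The trial collects variables that could explain missingness, notably the T00 and T02 counts. Under the rule as written, they enter the analysis only if somebody judges power to be a problem. A distorted main comparison could therefore be reported as unbiased by rule, in a pilot whose purpose (Section 3) is to inform a definitive trial.

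**Working it through.** **1. The plan's own figure.** From Section 10.5: difference 7 B-lines, effect size 0.7, 35 per arm, two-sided 0.05. The implied SD is 7 / 0.7 = 10. The two-sample t test (noncentral t) then has 82.3% power, which matches the stated 82%.

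**2. Why complete cases can be biased under MAR.** Let X be the T02 count and Y the T06 count, with equal SDs and correlation ρ, so that within an arm E(Y | X) = μ_Y + ρ(X − μ_X). If missingness of Y depends only on X, MAR holds. The mean of Y among observed patients is then μ_Y + ρ·s, where s is the mean of X among the observed minus the mean of X in the whole arm. Taking the difference as diuretic minus nitrate:

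complete-case difference = true difference − ρ(s_nitrate − s_diuretic).

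The bias vanishes if s is the same in both arms. It does not vanish merely because MAR holds.

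**3. Size, same missingness rule in both arms.** Assumptions, none of them given in the documents: bivariate normal counts, true T06 difference 7, SD 10 (implied by Section 10.5), ρ = 0.7–0.8, missingness 10–30% overall, and a logistic rule with slope 0.1–0.2 per B-line in which lower T02 counts are more often followed by a missing T06.

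| Assumed arm difference at T02 | Complete-case difference (truth 7) | Bias toward zero |
|---|---|---|
| 0 | about 7.0 | none |
| 3.5 | 6.2–6.8 | 0.2–0.8 |
| 5 | 5.8–6.8 | 0.2–1.2 |

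The largest bias comes from ρ = 0.8, slope 0.2 and 30% missing. There 7 − 5.8 = 1.2, so the observed T02 means have shifted apart by 1.2 / 0.8 = 1.5 B-lines.

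**4. No true effect.** With ρ = 0.5–0.7, slope 0.15 per B-line (1.5 per SD) and base missingness 20%:

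- The same T02 rule in both arms gives no bias and a type I error of about 5%.
- T02-dependent missingness in one arm only (27% missing against 20%) gives a false difference of 1.5–2.1 B-lines. Type I error is 7.6–11.1% in 3,000 simulated trials of 35 per arm.
- In the one-arm case, a binary outcome cut at the assumed control mean (an illustration, not the plan's threshold of 15) shows a risk difference of −0.06 to −0.08 when the truth is 0.

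**5. Does imputation remove it?** Arm-specific regression imputation on T02, which targets the same mean as MAR-based multiple imputation, gave 6.95–7.02 when the truth was 7 and stayed within 0.04 of 0 when the truth was 0. This is expected, because the imputation model contains the variable that drives missingness.

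**The case against.** Several objections carry weight.

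- **The primary test is not specified.** A reader might infer that the primary result itself is a t test that will be biased. Section 10.4.3 describes distributions, ROC curves, thresholds and a covariate-adjusted logistic regression, and names no two-sample test for the count. The t test is only implied by Section 10.5. Adjusted logistic or proportional-odds models would be less affected if they include what drives missingness. This stands, and it limits the point to the named unadjusted tests and the implied comparison.
- **The direction is not established.** A reader might infer that fast responders leave without a final scan, so that the better arm loses its best outcomes and the effect shrinks. The documents do not support that. Section 7.3.4 moves T06 forward to just before ED discharge. Section 4.1 ends the study protocol once B-lines fall to ≤ 15, and the Protocol Summary takes the endpoint at the end of ED management or 6 hours, whichever is first. A fast responder's early scan may already be the endpoint. Section 6.1.1 also has a recovery step, and patients who deteriorate could equally miss scans.
- **The size is modest.** At most 1.2 B-lines in the table compares with a standard error of 10 × √(2/35) = 2.4. The bias is nil if the arms do not differ at T02.
- **Imputation may happen anyway.** The sample size carries no dropout allowance. With 20% missing (28 per arm), t-test power falls to about 73%, so the power condition could easily be met. It remains a discretionary trigger.
- **The MNAR analyses are planned, and completers will be compared with dropouts.** Both are useful, but neither changes the rule for the main result under MAR.

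One could also read the use of all observed outcomes as a likelihood analysis of every scan. No such model is specified for B-lines: the mixed-effects model in Section 10.4.4 concerns observer variability.

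**Conclusion.** The concern holds in a limited form. The no-bias statement is not valid as a general guarantee for the unadjusted tests of B-lines ≤ 15, dyspnea change and DAOOH, nor for the two-sample B-line comparison implied by the power statement. Tying imputation to power alone leaves any such bias in place. It would go too far to call the statement false under every MAR pattern, since identical T02 distributions and missingness rules in the two arms give no bias in the difference.

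Under the stated assumptions the understatement runs from nothing to about 1.2 B-lines out of 7 (1.2 / 7 = 17%). The upper end needs a T02 arm difference of about 5, 30% missing, and the strongest correlation and slope tried. Missingness that depends on T02 in one arm only can raise the type I error above 5%. The documents give no missing-data rate, T02 difference or mechanism, so these figures show what the rule permits and do not predict what this trial will see.

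**What to change.** Replace the MAR sentences in Section 10.4.6 with wording such as:

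> Under MAR, between-arm comparisons of outcomes with missing values will use multiple imputation (PROC MI/MIANALYZE) including arm, hospital, T00 and T02 B-line counts and the other observed predictors of missingness, or an equivalent likelihood-based model, to limit bias as well as power loss, whatever the amount missing.

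Report complete-case results as supportive and keep the MNAR models as sensitivity analyses. The missing-data section should not be used to bring in a new primary model. The between-arm test for the primary count needs to be stated in Section 10.4.3.

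The cost is a change of SAP wording and slightly more analysis work. The B-line counts, arm and hospital are already collected, and the SAS procedures are already named in the plan.
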